### **2.3.2 Procedures to Minimize Risks**

Alcohol swabbing of the skin prior to venipuncture and IFN  $\beta$ -1a injection, and use of sterile disposable needles and syringes will minimize the risk of infection. Applying pressure over needle puncture sites to minimize bruising should also be carried out. Exclusion of patients who have previously experienced a severe allergic reaction to IFN  $\beta$  preparations, and since participants will probably remain in the treatment centres for the duration of treatment, trained personnel will be available in case for allergic reactions post-injection.

For the first ten (10) ebola-infected subjects to receive IFN  $\beta$ -1a, a staggered administration schedule will be used to minimize the effect of any unforeseen serious adverse events in this patient population. The second patient will not be administered IFN  $\beta$ -1a until the first subject has received five (5) doses. Likewise, the third subject will not be administered IFN  $\beta$ -1a until the second subject has received 5 doses. If, in the opinion of the treating physician and the Special Access Program in Conakry, Guinea, no unforeseen serious adverse events are observed five (5) days after the tenth subject has received IFN  $\beta$ -1a, more than one of the remaining

subjects enrolled/to be enrolled in the study may receive their first dose of IFN  $\beta$ -1a on the same day.

### **2.3.3 Potential Benefits**

This study offers a potential for antiviral therapy for patients with EBOV disease. Although IFN  $\beta$ -1a has not been administered to patients with EBOV infection, the clinical experience of IFN  $\beta$ -1a with another virus (HCV) demonstrates a favorable safety profile. Thus the major benefit of this study may be in helping patients with more severe EBOV disease to recover more rapidly, to prevent complications, and to prevent death.

The risks of this study are acceptable considering the known safety profile of the investigational product and the potential benefit to the patients is high, yielding a favorable risk-benefit ratio.

### **3. Investigators and Trial Organization**

The trial will be conducted by investigators in Conakry, Guinea. Centres will be selected based on interest to participate and ability to conduct this trial.

### **4. Hypothesis and Trial Objectives**

The study hypothesis is that IFN  $\beta$ -1a therapy will reduce viral load in Ebola-infected subjects, that IFN  $\beta$ -1a is safe to use in these individuals, and that the complications associated with EBOV infection can be prevented with IFN  $\beta$ -1a as a consequence of inhibiting viral replication.

The primary objective of this pilot study is to evaluate the effectiveness of IFN  $\beta$ -1a on viremia in peripheral blood of Ebola-infected subjects

The secondary objective is to evaluate the safety of IFN  $\beta$ -1a in Ebola-infected subjects

The tertiary objective is to determine whether IFN  $\beta$ -1a can prevent Ebola virus disease progression and/or on resolution of disease

### **5. Study Design**

This study is single-arm clinical trial with a pre- and post- study design. The study will include patients who are admitted with EBOV infection to a treatment centre. If a patient meets the inclusion criteria and gives informed consent (or informed consent is given by a substitute decision maker who is responsible for the patient due to the patient's illness), the patient will be enrolled into the study i.e. the first 30-50 eligible patients will be enrolled. Patients who receive IFN  $\beta$ -1a will be treated through the Special Access/Compassionate Release Program (consent to treatment through their treating physician) administered in Conakry, Guinea. This part of the study will collect data retrospectively, including results from research testing of (residual/to be discarded) blood samples. The study team can make available the systematic data collection forms to the treating physician to help in monitoring of adverse events and effect of therapy, enabling more specific reporting to the Special Access Program administered in Conakry, Guinea by the treating physician for patients receiving IFN  $\beta$ -1a.

As noted above, retrospective data collection will include patients with EBOV disease who do not participate in this clinical trial. Data from IFN  $\beta$ -1a-treated patients will be matched with data from patients who did not receive IFN  $\beta$ -1a, based on age, sex, estimated days post-onset of symptoms, and viral load (if available). This data collection is similar to that proposed in this protocol. Also, this protocol proposes to test blood collected clinically (residual or to be discarded) for comparisons between the groups in this interventional study.

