### **Pre- and post- Clinical Trial:**

The authority to approve a treating physician's access to IFN  $\beta$ -1a for treatment of patients under the Special Access Program, is based on a medical decision for treatment and a discussion between the treating physician and the patient (or the patient's substitute decision maker). The collection of safety and efficacy data for monitoring by the treating physician and reporting to [name] can be done based on the study case report. This will facilitate reporting by the treating physician and allow more specific and consistent reporting to [name].

This component of the study is to provide the ability to have special access to IFN  $\beta$ -1a if indicated clinically while providing consistent monitoring of adverse events and effect of therapy. Considering that some patients may continue to deteriorate despite antivirals or that they may be infected with an antiviral resistant strain, IFN  $\beta$ -1a will be made available to treating physicians for patients for whom the treating physician believes that there may be a benefit to giving IFN  $\beta$ -1a. Consent for treatment with IFN  $\beta$ -1a would be obtained by the treating physician. Monitoring of treatment will be important to ensure that any safety concerns are identified. Monitoring will include collecting information from the patient's chart as well as some research testing of residual samples which would otherwise be discarded. A template of the informed consent form is attached. The comparison group will be the group of patients who have EBOV disease and do not receive IFN  $\beta$ -1a.

Of note, it is recognized that there will likely be missing data on study participants due to retrospective data collection. Collection of data will be based on the clinical course and interventions required in the care of these patients.

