### 6.5 Follow-up

Collection from daily recordings will be undertaken either prospectively or retrospectively to assess adverse event and efficacy of therapy from day 1 (1st day of treatment) to day 10 and then weekly while admitted to the treatment centre and then 30 days post last dose. For patients for whom therapy is discontinued prior to day 10, assessments will follow the same schedule to allow comparison of disease course.

The following will be recorded, as permitted, starting immediately prior to the onset of administration of IFN  $\beta$ -1a, then on a daily basis whilst the patient is in the treatment centre:

- Temperature; fever will be defined as a temperature  $\geq 38$  °C.
- Concurrent illness symptoms: chills, myalgia, cough, sore throat, nausea, vomiting, diarrhea, hemaorrhage.
- Adverse events will be recorded per protocol. Medication history at baseline and daily will be recorded.
  - Blood samples:
    - 20 cc of Blood for virologic measurement (if feasible).
    - A convalescent serum (10 cc tiger top tube) will be obtained at 1 month (when possible).
  - Survival

Of note, it is expected that there will be missing data points for study participants depending on the clinical care data available in the medical chart and residual blood samples available for testing.

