### 8.3 Adverse Event Definitions and Reporting

Adverse Event (AE): is any untoward medical occurrence in a patient or clinical investigation participant administered a product. It does not necessarily have to have a causal relationship with this treatment. An AE can therefore be any unfavorable and unintended sign (including an abnormal laboratory finding, for example), symptom or disease temporally associated with the use of a medicinal product, whether or not considered related to the medicinal product.

All adverse events will be recorded and transcribed into the CRF. Solicited AEs and non-solicited AEs will be collected daily for the first four days and then every 2-3 days during therapy, or whenever reported by patients. SAEs will be collected while on study medication and for 30 days after administration of the last dose.

**Serious Adverse Event (SAE):** is any adverse event that:

- is fatal
- is life-threatening
- results in persistent or significant disability/incapacity
- requires initial hospitalization or prolongation of existing hospitalization
- causes congenital anomalies or birth defects

The term "life-threatening" refers to an event in which the patient was at risk of death at the time of the event. It does not refer to an event, which hypothetically might have caused death, if it were more severe. All deaths occurring while on protocol therapy or within 30 days of the last dose, should be reported (see below).

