### SAE Reporting

All SAEs must be reported within 24 hours to the Study Coordinator and to enable reporting to the Guinean Ministry of Health within 7 calendar days of identification. All SAEs must also be reported within 24 hours to BiogenIdec Inc. at [[contact]](mailto:[contact]) or by FAX at [contact].

All AEs and SAEs will be evaluated by the investigator or delegate for causal relationship to the investigational product.

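### The protocol sets incompatible modes for collecting safety data from IFN β-1a-treated patients, so neither solicited reactions nor prompt SAE reports are secured

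*Protocol*

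**What the plan says.** The protocol describes how treated patients' safety data are collected in several places.

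- **Section 5, first paragraph.** After the sentence on patients treated through Special Access: "This part of the study will collect data retrospectively, including results from research testing of (residual/to be discarded) blood samples". Then: "The study team can make available the systematic data collection forms to the treating physician to help in monitoring of adverse events".
- **Section 5, Pre- and post- Clinical Trial.** Using the study case report for safety reporting is again worded as an option, and "it is recognized that there will likely be missing data on study participants due to retrospective data collection".
- **Section 6.1.** Retrospective collection is assigned to the observational part of the study, and a comparison group is then named for that same part.
- **Section 6.5.** "Collection from daily recordings will be undertaken either prospectively or retrospectively to assess adverse event and efficacy of therapy". The items are to be recorded daily in the treatment centre, as far as circumstances permit.
- **Section 8.3.** "Solicited AEs and non-solicited AEs will be collected daily for the first four days", then every 2-3 days during therapy, with all adverse events transcribed into the CRF. Under SAE Reporting: "All SAEs must be reported within 24 hours to the Study Coordinator".
- **Section 9.2.** The secondary endpoint includes onset, duration and severity of solicited and non-solicited reactions up to 7 days after the last injection.
- **Section 11.** CRFs go into the clinical chart for direct documentation only if this is possible.

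**The concern.** A solicited event is one that somebody asked about at the time. If nobody asked, a later reading of the chart will miss mild reactions and seldom give their first and last day. A site that follows Section 5 complies with the protocol and yet cannot deliver what Sections 8.3 and 9.2 need.

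Safety is the secondary objective, and Section 16 makes it a determining factor for extending the trial to 100 participants. If some patients were asked on schedule and others were abstracted from charts, the safety summary would mix the two without a label. Under-recording could then pass for good tolerability. Prompt SAE reporting is also at stake, because it depends on someone noticing and transmitting the event during treatment.

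**Working it through.** The protocol has no figure of its own to reproduce here, so the check sets the passages side by side.

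**1. Does retrospective collection cover treated patients?** Probably, but the text does not settle it.

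- For: the Section 5 sentence follows the one on patients who receive IFN β-1a. The next paragraph says retrospective collection will also include patients outside the trial, which reads as an addition. Section 6.1 names a comparison group for this part, so the part seems to contain a treated group too. The Pre- and post- text speaks of missing data on study participants.
- Against: Section 6.1 uses the label observational, and Section 6.2 gives demographics as its example of retrospective data.

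**2. Which modes are stated for the same safety data?**

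| Place | Mode | Study form |
|---|---|---|
| Section 5, both parts | Retrospective | Optional |
| Section 6.5 | Either | Daily recording, as permitted |
| Section 8.3 | Scheduled during therapy; SAEs within 24 hours | CRF required |
| Section 11 | Direct documentation | In the chart if possible |

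These cannot all hold for one patient, and no sentence ranks them.

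**3. What does each safety element need?**

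- *Solicited reactions (9.2).* Onset, duration and severity need someone to ask during treatment. Retrospective collection without bedside solicitation cannot supply them. This is the strongest effect.
- *SAE reporting (8.3).* The 24-hour limit has no stated starting point, and the 7 days for the Ministry of Health run from identification. If both are read from identification, an SAE found at chart review and reported the next day complies, however long ago it happened.
- *Dosing gate (2.3.2).* Each step is triggered by a dose count: the preceding patient has received five doses. Release after the tenth patient requires that "no unforeseen serious adverse events are observed five (5) days after the tenth subject has received IFN" β-1a, in the opinion of the treating physician and the Special Access Program. The physician sees events directly. The Program depends on reports.
- *Stopping rule (8.4).* The trigger is one death during therapy from a related SAE. Staff at the bedside see the death.

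**4. Timing illustration for the stagger (collection lags are assumed).** Let first doses be 4 or 5 days apart, with patient 1 on day 1.

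- Patient 10 starts on day 1 + 9 × 4 = 37 or 1 + 9 × 5 = 46. Release falls five days later, on day 42 or 51.
- If a patient's study data were complete only at the end of a 10-day course (start day + 9), the next patient would start at start day + 4 or + 5. The preceding patient's data would then be complete at 0 of 9 steps. Patient 9's course ends on day 33 + 9 = 42 or 41 + 9 = 50, and patient 10's on day 46 or 55, so 9 of 10 patients would be complete at release.
- With real-time collection the preceding patient's data are in hand at 9 of 9 steps.

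A study form filled in retrospectively therefore could not inform the steps. Bedside observation still could.

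**The case against.** The best defence is that Section 6.5 separates recording from collection. Items are recorded daily at the bedside, and only their transfer to the study may come later. Section 8.3 is the specific safety section, applies to participants given the product, and should prevail over general wording in Section 5. Much of this stands: the plan is not uniformly retrospective, and a careful site could meet Section 8.3. But daily recording is only as permitted, the form is optional, and the protocol itself expects gaps due to retrospective collection. The contradiction remains, and a sponsor who meant comparison patients only would need the same edit.

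A reader might infer something stronger: that the dosing gate and the stopping rule act on data not yet collected. The documents do not support this. Dose counts, the treating physician's opinion and a death during therapy are all available at the bedside. What remains is narrower: the Special Access Program's part of the gate, and the direct comparison of groups in Section 8.4, depend on reported or abstracted data. Nor can one state how many patients would start before an event became known, or what share of events charts would miss. Both need an abstraction date and a capture rate that the protocol does not give.

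A second fair objection concerns the remedy. Closer recording in treated patients alone widens the difference in ascertainment from comparison patients, whose events come from charts. Restricting the 9.2 summary to solicited records would discard documented events from an endpoint that expressly covers both kinds. Both arguments stand, and the change below allows for them. The conditional wording also reflects limited resources in an outbreak. That justifies a short entry, but not leaving the mode undecided.

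**Conclusion.** The concern holds as a contradiction that should be corrected. For treated patients the protocol states retrospective, either-mode and scheduled collection of the same safety data, with a form that is optional in one place and required in another. The main consequence is for solicited reactions in Section 9.2, whose onset, duration and severity would be unreliable wherever Sections 5 and 6.5 are followed. The second is that SAE reports could be late and still compliant. The gate and stopping rule are affected only through reporting.

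No numerical size is claimed. The 0-of-9 and 9-of-9 contrast rests on assumed collection lags and describes study data, not what clinical staff know. The conclusion also rests on reading the retrospective sentence in Section 5 as including treated patients, which is the more natural reading but not a certain one.

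**What to change.** Reconcile Section 5 (both parts), 6.1, 6.5, 8.3 and 11 as follows.

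- For every IFN β-1a-treated patient, doses given, solicited and unsolicited adverse events, SAEs and vital status are recorded during treatment on the study CRF, with adverse events on the Section 8.3 schedule. The form is required.
- Retrospective collection is limited to comparison patients and to background items such as demographics.
- The 24-hour SAE limit runs from the time site staff become aware of the event.
- Each adverse event record is flagged as solicited or chart-derived. An event found in both sources carries both flags, which matters if the CRF is kept in the chart. Section 9.2 is reported by source, and all events are kept.
- The comparison with untreated patients in Sections 8.4 and 9.2 uses chart-derived events in both groups, so that closer recording of treated patients does not bias it.

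The cost is wording in five places, one flag variable and a short bedside entry that becomes compulsory on the existing schedule. Section 11 already plans for the CRF to sit in the chart, so no new form is needed. The like-sourced comparison will miss events that charts omit in either group, so it should be read alongside the full summary for treated patients.

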
Statistical Methods and Analyses
	
Endpoints will be described and compared between baseline and day 10, for the treatment group using cross-tabulation tables and Fisher's Exact test for categorical variables, t-test for normally distributed continuous variables, and Wilcoxon non-parametric test for non-normally distributed continuous or ordinal variables. Data collected will be compared with a retrospective analysis of age-matched Ebola-infected individuals who presented with similar symptoms (and viral loads) and who did not receive IFN <math>\beta</math>-1a.

	
Safety variables such as fever will be considered in three different formats:
 

1. As ordinal, representing various levels of severity of the AE. For instance, fever will be described as “none”, “mild”, “moderate” or “severe”.

2. As binary, considering only the presence vs. the absence of the AE.

3. As binary, considering the most serious expression of the AE. For instance by grouping “moderate” and “severe” together.

 
Separate analyses for time periods of 0-3, 4-7 and 8-10 days will be conducted. For each of these time periods the most severe report of the AE for each participant will be counted.
 
Adverse Events and Serious Adverse Events will be considered in two ways: presence of any event and presence of any event related to the treatment.
 
Viral clearance and symptom endpoints will be analyzed as binary variables for detection (presence) or non-detection (absence) as well as continuous variables where applicable (e.g.; quantitative RT-PCR measurements).

--	---

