### 1.2 Epidemiologic situation as of November 19, 2014 (WHO data)

In the context of this outbreak, this is the first outbreak in West Africa, therefore there is a lack of understanding within local communities, lack of experience among health care workers and limited capacity for rapid response. There is a high level of community exposure, a consequence of household care and customary burial procedures, leading to fear, panic and some resistance to proposed response measures. Close community ties across border areas are having an impact on care-seeking behaviors and contact tracing. The magnitude of the spread of this outbreak in the 3 most affected countries, as of November 19, 2014, is in rural areas and in large cities, (see Table 1), and requires an enormous commitment of resources and robust sustained response capacity.

There is no vaccine or specific approved treatment for EBOV disease currently available. At the present time, patients are only provided with usual supportive care on arrival at treatment centres. There are promising data related to novel vaccines and potential antiviral drugs, derived from *in vitro* and pre-clinical animal models of EBOV infection, yet these have not been evaluated for safety and efficacy in humans.

In the current context, the WHO has recommended that it is ethical to offer unproven interventions (with unknown efficacy and unknown adverse events) as potential treatments or prevention strategies. Any therapeutic intervention must be administered with informed consent and freedom of choice, the decision having been made following a thorough risk-benefit assessment, and respecting the confidentiality and dignity of the patient. In addition, there is a moral obligation to collect and share all data generated, to understand the safety and efficacy of any intervention, including a moral duty to evaluate any intervention in the best possible clinical trial feasible, and to inform future interventions.

Country	Cumulative cases (Conf-Prob)	Cumulative deaths
Guinea	2047	1214
Liberia	7082	2963
Sierra Leone	6190	1267

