### **6.1 Informed Consent Process**

#### **Clinical Trial:**

All participants (or substitute decision makers) must understand and sign the informed consent document. The Guinean physicians and associated health workers will play an important role in addressing cultural and ethical sensitivities associated with the treatment protocol, and the Guinean authorities have indicated they will assume responsibility for disseminating information about the nature of clinical trials aimed at treating Ebola virus disease.

The observational part of the study will collect data retrospectively, and results from research testing of (residual/to be discarded) blood samples and respiratory secretions.

The comparison group for this part of the study will in part be the population that may be included in an existing epidemiologic study for which there is a waiver of consent. For patients

in the comparison group who were not enrolled in such a study where waiver of consent was applied, all reasonable efforts will be made to obtain informed consent where that individual's data will be used. However, it should be noted that obtaining informed consent from a non-IFN  $\beta$ -1a-treated patient who survived the ebola infection and left the clinic may be difficult to obtain, as it may be from the relatives of those non-IFN  $\beta$ -1a-treated patients who died following ebola infection. Retrospective data collection and testing will be as consistent as possible with the clinical trial data collection form, depending on data available from medical records. Research testing will be performed on the blood and secretions samples (residual or to be discarded).

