### **15. Time Frame for the Study**

Given the nature of this EBOV outbreak, it is difficult to predict the waves and the study may span more than one wave, and thus it is difficult to determine the actual time to complete the study.

Since this is a pilot study, it is important to have such a protocol in readiness so that, new cases can be immediately enrolled. It is estimated that during a wave, it will be possible to recruit 30 participants, in less than one month. It is planned to propose the study to be conducted at other treatment centres across West Africa. The rationale is to increase the rate of enrolment for the pilot study so that if a potential benefit is detected early, IFN  $\beta$ -1a therapy can be evaluated

relatively rapidly, in an effort to make it available, through the extended study (and possibly a larger multicentre international study) as part of the treatment armamentarium as early as possible.

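### Untreated comparators are not matched or restricted by treatment centre, country or admission period, so differences between places or periods could be read as a drug effect

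*Protocol*

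**What the plan says.** Section 5 describes a single-arm pre/post study, then adds a retrospective group of untreated patients matched "based on age, sex, estimated days post-onset of symptoms, and viral load (if available"). The synopsis words the rule differently: "Data collected will be compared with a retrospective analysis of age-matched Ebola-infected individuals who presented with similar symptoms", with viral loads added in brackets.

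The subsection of Section 5 on the pre- and post- trial defines the group broadly: "The comparison group will be the group of patients who have EBOV disease and do not receive IFN" beta-1a. Section 6.1 says that it "will in part be the population that may be included in an existing epidemiologic study", and gives neither the place nor the dates of that study.

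On where and when treatment happens, Sections 3 and 6 place the trial in Guinea. Section 15 adds that "the study may span more than one wave" and that "It is planned to propose the study to be conducted at other treatment centres across West Africa".

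The untreated group is used in several places. Section 8.4 compares safety directly with it. Section 9.3 compares all-cause death between the groups. Section 10.2 tests categorical endpoints with Fisher's exact test and survival with Kaplan-Meier and Cox methods, naming no covariates or strata. Section 16 bases the extension to 100 on safety and, if the small sample allows, an efficacy trend against standard of care.

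**The concern.** Treatment is not randomised, so the choice of comparators is the main protection against confounding in every between-group statement. The protocol fixes that choice itself, by listing the matching factors. This is therefore a stated rule and not a detail left for a later analysis plan.

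As written, the rule lets a treated patient be paired with someone from another centre or an earlier wave, and does not exclude another country. Age, sex and days of illness do not carry information on place or period. Viral load might carry some of it through severity, but it is matched only where it is available, and Sections 5 and 6.5 expect missing data.

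If mortality, adverse-event recording or completeness of follow-up differs between centres or periods, the difference is attributed to IFN beta-1a. Section 16 looks for a trend and does not require a significant result, so even a modest imbalance could influence the decision to extend.

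**Working it through.** **No plan figure to reproduce.** Section 10.1 chooses 30-50 patients for feasibility and gives no power inputs.

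**Inputs.** Section 1.2, Table 1, introduced with "The magnitude of the spread of this outbreak in the 3 most affected countries", gives cumulative deaths over confirmed and probable cases:

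- Guinea: 1214/2047 = 59.3%
- Liberia: 2963/7082 = 41.8%
- Sierra Leone: 1267/6190 = 20.5%
- All three: (1214 + 2963 + 1267)/(2047 + 7082 + 6190) = 5444/15319 = 35.5%

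The group size is 30 or 50 treated patients (Section 10.1) and the test is Fisher's exact test (Section 10.2). Assumptions not in the protocol: two-sided alpha 0.05, one comparator per treated patient, and Table 1 ratios standing in for mortality in each group.

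**Formula.** Let the drug be inert, and let pT and pC be the mortality of the treated and comparator groups, each of size n. The chance of a significant result is the sum, over all death counts i and j with Fisher p ≤ 0.05, of Bin(i; n, pT) × Bin(j; n, pC). Results with more treated deaths count as false harm and those with fewer as false benefit.

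**Results.**

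| Treated vs comparators | pT vs pC | Direction | n = 30 | n = 50 |
|---|---|---|---|---|
| Same mortality | 59.3% vs 59.3% | either | 2.6% | 3.2% |
| Guinea vs three-country pool | 59.3% vs 35.5% | false harm | 36.2% | 61.5% |
| Liberia vs Guinea | 41.8% vs 59.3% | false benefit | 19.7% | 36.2% |
| Sierra Leone vs Guinea | 20.5% vs 59.3% | false benefit | 82.6% | 97.5% |

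The first row is what same-centre, same-period matching aims for. It splits evenly, with 1.3% (n = 30) or 1.6% (n = 50) in each direction.

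**Within Guinea.** The protocol gives no figures for differences between centres or periods, so the size is assumed. If such a difference lowers mortality in the treated group below 59.3%, false benefit appears as follows:

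| Assumed difference | n = 30 | n = 50 |
|---|---|---|
| 5 points | 3.4% | 5.3% |
| 10 points | 7.6% | 13.3% |
| 15 points | 14.8% | 27.3% |
| 20 points | 25.7% | 46.2% |

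**The case against.** The strongest reply is that the cross-country scenarios are not the protocol's plan. Investigators, drug access and regulatory reporting are all in Guinea. No section says that comparators come from Liberia or Sierra Leone. Two features point to local comparators: their leftover clinical samples are to be tested (Sections 5 and 6.1), and consent is to be sought from untreated survivors who have left the clinic or from relatives of those who died (Section 6.1). This stands. The protocol fails to exclude foreign comparators; it does not plan them.

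A reader might infer from Table 1 that an inert drug could as easily look life-saving as lethal. The documents do not support that symmetry. Guinea has the highest ratio, so foreign comparators for Guinea patients could only make the drug look worse. False benefit needs centres outside Guinea whose patients are matched to Guinea comparators, or differences within Guinea that Table 1 does not measure. Section 15 speaks only of proposing the study to other centres.

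A reader might also treat Table 1 as centre mortality. It is a crude mid-outbreak count, not limited to resolved cases, admitted patients, ages 18 to 69 or early presenters. Section 1.1 gives fatality for this virus as 57-90%, and the Liberia and Sierra Leone ratios lie below that range. Part of the spread may therefore be unresolved cases or uncounted deaths, and nothing shows that individual medical records share those gaps. Likewise, Section 6.2 says that baseline investigations depend on each centre's resources; it does not say that care does.

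Finally, death is a tertiary endpoint in a pilot whose primary endpoint is viral load, on which Table 1 is silent, and Section 16 does not rest on a Fisher test of mortality. This lowers the severity. It does not close the gap: even within Guinea, the matching list ignores centre and wave.

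**Conclusion.** The concern holds in a limited form. The stated matching rule leaves between-group comparisons of survival, safety and efficacy trend open to confounding by place and period, and no other section closes that gap.

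Its size cannot be fixed from the protocol. The 36% to 62% chance of false harm is a hypothetical bound. It assumes comparators drawn from three countries in proportion to reported cases, crude ratios taken as true mortality, two-sided alpha 0.05 and 1:1 matching. The nearer problem is a centre or wave difference within Guinea. An assumed 10-point difference raises the chance of false benefit to 8% to 13%, against 1.3% to 1.6% when both groups have the same mortality.

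The primary virological comparison may be affected too, but the documents give no basis for a figure. The change should be made; the documents do not support calling the flaw fatal to the pilot.

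**What to change.** In Section 5 and the synopsis, use one and the same matching rule, and state that:

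- comparators come from the same treatment centre as the treated patient;
- admission date is a matching factor with a stated window, which may include the period just before IFN beta-1a became available at that centre;
- comparators meet the trial's eligibility criteria;
- any centre that joins later supplies its own comparators, and analyses are stratified by centre;
- the reason why each concurrent comparator was not treated is recorded.

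This is mainly wording, since centre and admission date should already be in the charts. It does have a price. The pool shrinks, so matches on age, days of illness and viral load become looser. There is also a risk of exchanging one bias for another. Because the first 30-50 eligible patients are to be enrolled, untreated patients at the same centre and time may largely be refusers or patients not selected for treatment. That is why the window should be allowed to reach back before the drug became available, and why the reason for non-treatment is needed.
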